#### **4.2 Visit schedule and analysis windows**

Clinic visits take place at screening, entry (which may be the same day as screening), and Weeks 4, 12, 24, 36, and 48. All measures on or before the randomization date are grouped as Week 0,

with the value closest to and on or before the randomization date used as the baseline measurement. Scheduled visit windows for the week 4 and 12 visit is  $\pm$  14 days and for weeks 24, 36 and 48 the window is  $\pm$  28 days. Analysis visit windows will be formed around each study visit using the midpoints between adjacent weeks as cutoffs. If there are multiple evaluations within the window for a given visit, the evaluation closest to the scheduled study week will be used.

#### 4.3 Outcome measure definitions

Primary objective: To estimate and compare HIV virologic suppression rates in YLWH 12 weeks after initiating TERA or continuing SOC.

This analysis will exclude participants dying before Week 12 for reasons unrelated to HIV.

Outcome measures:

- i. HIV-1 RNA <50 copies/ml. Participants with HIV-1 RNA  $\geq$  50 copies/ml or with no HIV-1 RNA measurement within the Week 12 window ( $\pm$  14 days) will be classified as failures
- ii. HIV-1 RNA < 200 copies/ml. Participants with HIV-1 RNA  $\geq$  200 copies/ml or with no HIV-1 RNA measurement within the Week 12 window ( $\pm$  14 days) will be classified as failures

Secondary objectives:

1. To estimate and compare virologic suppression rates in YLWH 24, 36, and 48 weeks after initiating TERA or continuing SOC.

These analyses will exclude participants dying before Week 24 (36, 48) for reasons unrelated to HIV.

Outcome measures:

- i. HIV-1 RNA < 50 copies/ml. This analysis will only include participants with the opportunity to reach the targeted study visit prior to the COVID study pause. Participants with HIV-1 RNA  $\geq$  50 copies/ml, or who had the opportunity to reach the study visit week and with no HIV-1 RNA measurement within  $\pm$  28 days of the scheduled visit, will be classified as failures
- ii. HIV-1 RNA < 200 copies/ml. This analysis will only include participants with the opportunity to reach the targeted study visit prior to the COVID study pause. Participants with HIV-1 RNA  $\geq$  200 copies/ml, or who had the opportunity to reach the study visit week and with no HIV-1 RNA measurement within  $\pm$  28 days of the scheduled visit, will be classified as failures

2. To estimate and compare proportions of participants initiating TERA or continuing SOC who achieve virologic suppression (HIV-1 RNA < 200 copies/ml) by 12 weeks and maintain virologic suppression through 48 weeks.

This analysis will exclude participants dying before Week 48 for reasons unrelated to HIV.

Outcome measure:

- i. HIV-1 RNA < 200 copies/mL at Weeks 12, 24, 36 and 48. This analysis will only include participants with the opportunity to reach Week 48 prior to the COVID study pause. Participants will be classified as virologic successes if the Week 12 ( $\pm$  14 days) and 48 ( $\pm$  28 days) HIV-1 RNA measurements are < 200 copies/mL and at least one of the Week

24 ( $\pm$  28 days) and Week 36 ( $\pm$  28 days) HIV-1 RNA measurements is < 200 copies/mL. Participants will be classified as failures if (1) either of the Week 12 or 48 HIV-1 RNA measurements are  $\geq$  200 copies/mL, (2) HIV-1 RNA at both Week 24 ( $\pm$  28 days) and Week 36 ( $\pm$  28 days) are  $\geq$  200 copies/mL, (3) both the HIV-1 RNA measurements between Weeks 12 and 48 are missing, or (4) either or both the Week 12 and Week 48 HIV-1 RNA are missing.

3. To summarize and compare adherence patterns in YLWH initiating TERA or continuing SOC during on-intervention period (week 0-12) and post intervention period (week >12-48).

Outcome measures:

- i. Electronic dose monitored adherence: Percent of days with dose taken per week
- ii. Electronic dose monitored on-time adherence: Percent of days with dose taken within the defined acceptable windows ( $\pm$  4 hours) per week.
- iii. Electronic dose monitored non-persistence: Number of gaps (at least 7 consecutive days (168 hours) between doses) in the intervals: week 0-12, >12-24, >24-36 and >36-48.

## 5 Primary outcome measure analysis: short term virologic success at Week 12

The primary objective of the study is to estimate and compare HIV virologic suppression rates (HIV-1 RNA < 50 copies/ml and <200 copies/ml) 12 weeks after initiating the TERA intervention or continuing SOC. If more than one HIV-1 RNA measurement occurs within the allowable 28-day window, the highest value will be chosen. Other than participants dying for reasons unrelated to HIV before Week 12, all eligible participants will be included in this analysis, classifying those lost-to-follow-up as failures. Sensitivity analyses will repeat the primary analysis (i) using observed HIV-1 RNA only (participants with missing week 12 HIV-1 RNA not included in denominator), (ii) using a wider window around the Week 12 study visit, and (iii) using last observed HIV-1 RNA if missing week 12.

Virologic success rates in each arm and the difference in success rates between arms will be summarized with 95% confidence intervals (CIs). Analyses adjusting for covariates identified *a priori* by the study team will be conducted to assess whether the magnitude and strength of the association between the intervention and virologic success changes after adjustment for other factors.

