## 2 Protocol Overview

### 2.1 Study Design

TERA is a Phase II, randomized, open-label study designed to assess the effectiveness of a Triggered Escalating Real-Time Adherence (TERA) intervention for 12 weeks in Youth Living With HIV (YLWH) failing antiretroviral therapy (ART). This time-limited approach includes education and motivational skills building from an adherence coach and monitoring with wireless electronic dose monitoring (EDM), for identification of delayed and missed doses of antiretrovirals and related alerts and coach phone-based outreach.

The original design was to enroll 120 YLWH, stratify by age (<18 years vs.  $\geq$ 18 years), and randomize with equal probability to TERA or continuing standard-of-care (SOC) for adherence. At entry, half were randomly selected to engage in additional in-depth interviews about their experiences at Weeks 12 and 48, with the goal of having 40 evaluable participants at both time points. Participants were followed for 48 weeks.

In August 2019, the Adolescent Trials Network Safety Monitoring Committee (SMC) recommended that accrual be closed and the 89 enrolled participants continue follow-up to study completion.

In March 2020, study visits were paused due to the outbreak of COVID-19. The study team decided to use the 'pre-COVID' database to analyze the primary and secondary objectives, since data collected after study visits resumed would be inherently different. This required a change to the definition of the virologic secondary outcome measures. It also meant that sample sizes at later study visits would be lower than anticipated, with a corresponding reduction in power to detect differences between arms. Additional data may be collected at study visits that take place after sites re-open. Analysis of these data will be outlined in a separate SAP.

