### **4 Statistical Methods**

#### **4.1 General considerations**

Baseline characteristics will be summarized by arm, but with no statistical comparisons. In general, categorical data will be summarized using N (%) and continuous data using N, key quantiles, and mean (STD) when appropriate.

Because of the interruption in study visits due to the COVID-19 pandemic in March 2020, analyses of the primary and secondary objectives will use the ‘pre-COVID’ study database including all data collected before study visits were paused. By March 2020, all participants had had the opportunity to reach Week 12, so analyses of the primary outcome measures were unaffected. However not all participants had had the opportunity to reach the Week 24, 36 and 48 timepoints. Only participants with the opportunity to reach each timepoint prior to the COVID-19 study pause will be included in assessments of the secondary outcome measures.

As this is a Phase II study, there are no *a-priori* statistical stopping guidelines. Statistical tests (all two-sided) will not be adjusted for interim monitoring, multiple comparisons or stratification for age. Significance levels  $p < 0.05$  will be highlighted in the text, but must be interpreted with caution since there will be many tests. Any changes to outcome measures after the analysis has begun will be identified as *post hoc*.

This Phase II clinical trial is not subject to NIH requirements that primary analyses of intervention comparisons be summarized by sex and race.

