## 6 Secondary outcome measures analysis

### 6.1 Longer-term virologic success at Weeks 24, 36 and 48

This outcome measure addresses virologic success rates after completion of the TERA intervention at Week 12, to assess the duration of its effect. The analytic approach will be similar to the primary outcome measure outlined in Section 5, conducting comparisons by arm at Weeks 24, 36 and 48, but with wider allowable windows ( $\pm$ 28 days) around each study visit, and excluding participants who die for reasons unrelated to HIV before each timepoint. If more than one HIV-1 RNA measurement occurs within the allowable 56-day window, the highest value will be chosen. Sensitivity analyses will repeat the primary analysis (i) using observed HIV-1 RNA only (participants with missing week HIV-1 RNA not included in denominator), (ii) using a wider window around the study visit, and (iii) using last observed HIV-1 RNA. An analysis combining data from Weeks 24, 36 and 48 will use generalized linear models to account for the repeated measures for each participant.

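### Inclusion at Weeks 36 and 48 is judged at the visit week, but the RNA window runs 28 days longer, so some participants are scored as failures only because the COVID pause cut their window short

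*SAP*

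**What the plan says.** Four statements in the SAP act together.

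- **Data cut.** Section 4.1 uses the "study database including all data collected before study visits were paused". Section 2.1 dates the pause only by month: "In March 2020, study visits were paused due to the outbreak of COVID-19".
- **Inclusion.** Section 4.1: "Only participants with the opportunity to reach each timepoint prior to the COVID-19 study pause will be included in assessments of the secondary outcome measures". Section 4.3 repeats this for each threshold: "This analysis will only include participants with the opportunity to reach the targeted study visit prior to the COVID study pause".
- **Window.** RNA counts within 28 days either side of the scheduled visit. Section 6.1 confirms the total width: "If more than one HIV-1 RNA measurement occurs within the allowable 56-day window, the highest value will be chosen". Section 4.2 gives the same 28 days either side as the scheduled visit window, so a visit up to 28 days late is on schedule.
- **Missing data.** Section 4.3 classes as a failure anyone above the threshold, "or who had the opportunity to reach the study visit week and with no HIV-1 RNA measurement within" 28 days of the visit. For sustained suppression, inclusion requires the opportunity to reach Week 48, and failure criterion (4) applies if "either or both the Week 12 and Week 48 HIV-1 RNA are missing".

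The SAP nowhere requires the late side of the window to have elapsed before the pause, and nowhere exempts a value that is missing because visits stopped.

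**The concern.** The opportunity restriction was added so that participants would not be penalized for visits the pandemic made impossible. It is tied to the visit week, whereas the outcome is tied to a window that closes 28 days later. Between those two dates lies a 28-day band of randomization dates. Participants in the band are in the denominator but did not have their full window. Any of them still unseen when visits stopped is a failure by rule, although they had not missed a visit by the SAP's own visit schedule.

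This puts some administrative missingness back into the main analysis of the Week 36, Week 48 and sustained-suppression outcomes. Section 2.1 already acknowledges that samples at later visits are reduced. The combined model for Weeks 24, 36 and 48 in Section 6.1 would inherit the coding if it uses the same outcome definitions.

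**Working it through.** The SAP states no figure on this point, so there is none to reproduce. The check is calendar arithmetic.

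**Inputs from the SAP:** 89 enrolled and closure of accrual recommended in August 2019 (Section 2.1); window of 28 days either side (Section 4.3), and 2 × 28 = 56 days agrees with Section 6.1.

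**Assumptions:** pause on 20 March 2020 (Section 6.3.1 gives this date for the adherence imputation only); even accrual ending 31 August 2019 and lasting 12 to 20 months (the SAP gives no accrual period).

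**Step 1: exposed randomization dates.** The visit week is reached if randomization + 7w days ≤ pause. The window has closed if randomization + 7w + 28 days ≤ pause. The exposed band lies between the two limits.

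| Visit | Reached if randomized by | Window closed if randomized by | Exposed band |
|---|---|---|---|
| Week 24 | 4 Oct 2019 | 6 Sep 2019 | 7 Sep to 4 Oct 2019 |
| Week 36 | 12 Jul 2019 | 14 Jun 2019 | 15 Jun to 12 Jul 2019 |
| Week 48 | 19 Apr 2019 | 22 Mar 2019 | 23 Mar to 19 Apr 2019 |

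The Week 36 and Week 48 bands precede August 2019, and they still do for any pause date from 1 to 31 March. The Week 24 band falls after accrual was to close. A participant randomized on 31 August 2019 has a Week 24 target of 15 February 2020 and a window closing on 14 March 2020. Week 24 is touched only if visits paused before about 14 March (a 1 March pause exposes randomizations after 18 August 2019) or if enrolment ran past August.

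**Step 2: number exposed, both arms together.** Accrual rate × 28/30.4375 months.

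- 12 months: 89/12 = 7.42 per month; 7.42 × 0.920 = 6.8
- 20 months: 89/20 = 4.45 per month; 4.45 × 0.920 = 4.1

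Evaluable n = 89 − rate × (days from the cut-off to 31 August 2019)/30.4375.

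- Week 36 (50 days): 76.8 to 81.7, so the band is 8.9% to 5.0% of those evaluable
- Week 48 (134 days): 56.3 to 69.4, so the band is 12.1% to 5.9%

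**Step 3: number misclassified.** Everyone in the band had the 28 days before target and between 0 and 28 days after it, on average 28 + 14 = 42 of 56 days (75%).

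- Attendance even across the window (assumed): 25% unseen, 0.25 × 4.1 to 6.8 = 1.0 to 1.7 participants
- All attendance after target, evenly spread (assumed): 50% unseen, 0.50 × 4.1 to 6.8 = 2.0 to 3.4 participants

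**Step 4: effect on the rate.** With an assumed true success rate of 40%, the fall is 0.40 × unseen fraction × band share.

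| Visit | 25% unseen | 50% unseen |
|---|---|---|
| Week 36 | 0.5 to 0.9 points | 1.0 to 1.8 points |
| Week 48 | 0.6 to 1.2 points | 1.2 to 2.4 points |

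**Step 5: chance shift between arms.** Half of 56.3 to 69.4 is about 28 to 35 per arm at Week 48. One participant who would have been a success but is scored a failure moves that arm's rate by 1/35 to 1/28, or 2.9 to 3.6 points. For comparison, with an illustrative 33 per arm and success near 44%, the standard error of the difference is √(2 × 0.44 × 0.56/33) = 12.2 points, giving a 95% interval of about ±24 points.

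**The case against.** **The SAP already has sensitivity analyses that bear on this.** Section 6.1 repeats the analysis on observed RNA only, and with the last observed RNA. The first removes every pause-truncated failure and the second replaces it with an earlier value. Section 6.2 analyzes the sustained outcome in the same way as the primary outcome, so it arguably inherits the equivalents in Section 5. This stands as mitigation. But observed-only also drops genuine losses to follow-up and so cannot isolate the pause, and last-observed substitutes a result from another visit. The wider-window analysis recovers nothing after the pause because the database ends there. The main analysis keeps the failure coding.

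**Opportunity is not operationally defined, and the separate Analysis Implementation Plan may settle it.** It may. As worded, though, the SAP points to the visit week, and it gives no pause day for the virologic outcomes. Two careful analysts could arrive at different denominators. SAP version 3.0 took effect on 24 June 2020, when the date was known.

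**Cutting at the target week is defensible because that is when the visit is scheduled.** It would be, if the window for a valid RNA did not also run 28 days past it.

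**Stronger readings that the SAP does not support.** A reader might infer that all 4 to 7 exposed participants are misclassified; only those unseen before the pause are, and some of them might never have attended. A reader might also infer a bias toward one arm; the calendar cut is common to both randomized arms, so the expected effect is lower rates in both and slight dilution of the difference. Nor does the problem reach the primary outcome: Section 4.1 says all participants could reach Week 12, and even a 31 August 2019 randomization has a Week 12 window closing on 7 December 2019.

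**Conclusion.** The point holds on the SAP's wording for Week 36, Week 48 and sustained suppression: inclusion, outcome window and data cut do not line up, and missing counts as failure. The size is modest. About 4 to 7 participants per timepoint across both arms are exposed and perhaps 1 to 3 misclassified, which lowers reported suppression by about 1 to 2 points in both arms. An uneven split by chance could move the observed difference by some 3 points per participant, well inside the sampling error.

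These sizes rest on a 20 March 2020 pause, even accrual over 12 to 20 months ending in August 2019, 25% to 50% of the band unseen, and 40% true success. The mechanism rests on none of them. The rule should be corrected because the change is small and the error defeats the stated purpose of the COVID restriction. It does not threaten the trial's main conclusion.

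**What to change.** State the pause date for the virologic outcomes, and define opportunity by dates alone: randomization date + target week + 28 days falls on or before the last day before visits were paused. Apply this to Weeks 36 and 48 and to the sustained outcome (using Week 48), and to Week 24 for consistency, where it should change little. Keep missing = failure only for participants who meet the rule. Retain the visit-week cut as a sensitivity analysis.

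The rule should not depend on whether an RNA value exists. Dropping only the unmeasured participants in the band would save data, but it would select on early attendance.

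The cost is a sentence or two in Section 4.3 and, under the accrual assumptions above, about 4 to 7 participants per timepoint, some with a valid early-window value. Evaluable numbers would fall from about 77–82 to 70–78 at Week 36 and from about 56–69 to 50–65 at Week 48. If analysis has already begun, Section 4.1 requires the change to be identified as post hoc.

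### The main Week 12 comparison is unadjusted, even for the age stratum, and covariate adjustment is kept for a does-it-change check with no covariates, model or effect scale named

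*SAP*

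**What the plan says.** - **Main comparison (SAP Section 5).** The result is the success rate in each arm, and "the difference in success rates between arms will be summarized with 95% confidence intervals". No covariate enters this contrast.
- **Tests (SAP Section 4.1).** "Statistical tests (all two-sided) will not be adjusted for interim monitoring, multiple comparisons or stratification for age". Results with p below 0.05 "will be highlighted in the text, but must be interpreted with caution since there will be many tests".
- **Adjusted analyses (SAP Section 5).** The study team will choose covariates a priori. The only stated purpose is "to assess whether the magnitude and strength of the association between the intervention and virologic success changes after adjustment for other factors". The covariates are not listed, and no model or effect measure is given. Baseline HIV-1 RNA is neither named nor excluded.
- **Baseline values (SAP Section 4.2).** Measures on or before randomization are grouped as Week 0, "with the value closest to and on or before the randomization date used as the baseline measurement". This is a general rule and does not mention HIV-1 RNA.
- **Design (SAP Section 2.1).** "The original design was to enroll 120 YLWH, stratify by age" and "randomize with equal probability to TERA or continuing standard-of-care (SOC) for adherence". In August 2019 the safety monitoring committee "recommended that accrual be closed and the 89 enrolled participants continue follow-up to study completion".
- **Later timepoints (SAP Sections 6.1 and 6.2).** The Section 5 approach is carried to Weeks 24, 36 and 48 and to sustained suppression.

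**The concern.** There are two separate issues.

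**Efficiency.** Randomization was stratified by age, but the comparison ignores age. The main contrast also uses no baseline value of the outcome, although participants enter while failing ART and a baseline HIV-1 RNA is therefore likely to exist (an assumption). With 89 participants the interval is wide. Adjustment for a prognostic baseline value could narrow it without new data and without changing what is estimated.

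**Interpretation.** Asking whether the association changes after adjustment is the logic of an observational study. Arm is randomized, so a change reflects chance imbalance or, on the odds ratio scale, non-collapsibility. With no effect scale fixed, a crude risk difference could be set beside an adjusted odds ratio and the shift read as a stronger or previously confounded effect. Nor does choosing covariates a priori ensure that they are measured before randomization.

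**Working it through.** The SAP states no success rates, effect size, power or precision target, so it has no figure to reproduce. What follows is an illustration.

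**Inputs from the SAP:** 89 enrolled of 120 planned, equal allocation, two-sided tests, 0.05 threshold, risk difference with 95% CI.

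**Assumed inputs:** a 45/44 split; success of 25% (SOC) and 45% (TERA); one standardised normal baseline covariate, independent of arm, with log-odds slope b per SD of 0, 0.5, 1.0 or 1.5.

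**Step 1. Crude precision.** SE = √[p₀(1−p₀)/n₀ + p₁(1−p₁)/n₁].

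- 45/44: √(0.1875/45 + 0.2475/44) = 0.099. The half-width is 1.96 × 0.099 = 0.194, about 19 percentage points. Power, with the pooled variance under the null, is about 51%.
- 60/60: √(0.1875/60 + 0.2475/60) = 0.085. The half-width is about 17 points and power about 64%.

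**Step 2. Gain from one baseline covariate.** With 1:1 allocation, the large-sample variances (times N) are:

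- Crude: 2p₁(1−p₁) + 2p₀(1−p₀).
- Adjusted: 2E[p₁(X)(1−p₁(X))] + 2E[p₀(X)(1−p₀(X))] + Var[p₁(X)−p₀(X)].

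The equivalent crude sample size is 89 divided by the unrounded ratio. As a finite-sample check, 4000 simulated trials of 89 compared the raw difference with the standardised difference from a logistic working model.

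| b | Variance ratio, large sample | Equivalent N | Variance ratio, simulated |
|---|---|---|---|
| 0 | 1.00 | 89 | 1.02 |
| 0.5 | 0.95 | 94 | 0.96 |
| 1.0 | 0.84 | 106 | 0.85 |
| 1.5 | 0.73 | 122 | 0.73 |

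Since half-width scales with the square root of the ratio, 19.4 points becomes about 18.9, 17.8 and 16.6 at b = 0.5, 1.0 and 1.5 (for example 19.4 × √0.843 = 17.8).

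**Step 3. Does the estimate change without confounding?** The marginal odds ratio is (0.45/0.55)/(0.25/0.75) = 2.45 throughout.

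| b | Conditional odds ratio | Trials where adjusted and crude odds ratios differ by more than 10% |
|---|---|---|
| 0 | 2.45 | 8% |
| 0.5 | 2.57 | 38% |
| 1.0 | 2.92 | 72% |
| 1.5 | 3.48 | 87% |

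The last column mixes chance imbalance with non-collapsibility. Neither is confounding by design. In the same trials the mean risk difference was 0.20 both crude and standardised.

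**Step 4. A second set of assumptions.** Here success is 25% v 50%, the baseline log10 RNA SD is 0.9, and baseline RNA predicts success with AUC 0.62, 0.71 or 0.78 (3000 trials each).

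- Variance ratios were 0.96, 0.90 and 0.79.
- Power moved from about 70% to 72%, 75% and 80%.
- Under 35% v 35%, rejection was 5-6% for both analyses.
- The marginal odds ratio of 3.00 became 3.16, 3.50 and 4.12 conditionally.

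**Limits.** Each simulation used one covariate. The effect of adding the age stratum was not computed, because the SAP gives nothing on how age predicts success. Section 4.3 counts a missing Week 12 HIV-1 RNA as failure. Baseline RNA need not predict missed visits, so the larger gains may be optimistic.

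**The case against.** The strongest case for leaving the plan alone is that an unadjusted risk difference is valid and openly declared, and that a supportive adjusted analysis beside it is ordinary practice. The choice between them is one of efficiency. That stands, and several stronger readings a reader might reach fail for related reasons.

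- **That the primary estimate is biased.** It is not. Randomization protects the crude difference.
- **That the precision in baseline HIV-1 RNA has certainly been given up.** The SAP does not show this. The unlisted covariates may include it, and Section 1.1 places table outlines and coding descriptions in a separate Analysis Implementation Plan. What is certain is that the main contrast does not use it.
- **That the plan will report an inflated odds ratio or claim confounding.** Section 5 names only the difference in success rates, no logistic model, and never mentions confounding. The odds ratio shifts in the working apply only if that scale is chosen.
- **That post-randomization covariates are planned.** Nothing says so. The text merely fails to exclude them.

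A further objection is timing. SAP version 3.0 took effect in June 2020, and Section 4.1 says all participants had had the opportunity to reach Week 12 by March 2020, in an open-label trial. Changing the main estimator that late invites criticism. Keeping the crude difference visible and dating the change answers most of this, but the timing must be stated openly.

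**Conclusion.** The point holds as a recommended improvement. It is not an error in the primary estimate. The main Week 12 contrast ignores the one covariate with a documented role in the design, and adjustment is given a purpose that does not suit a randomized comparison, with covariates, model and scale left open.

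Over the assumed range, the simulated effect of adjustment runs from a loss of about 2% of variance to a gain of about 4-27%. In large-sample terms the gain is worth about 5 to 33 extra participants (94 − 89 to 122 − 89). The size depends on success rates and prognostic strength that the documents do not give, and on baseline HIV-1 RNA being available. That a change after adjustment is not evidence of confounding follows from randomization and needs none of these assumptions.

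**What to change.** 1. **Section 5, main estimate.** Pre-specify the Week 12 risk difference adjusted for baseline log10 HIV-1 RNA and age stratum: a logistic working model with arm and both covariates, standardised over all participants analysed, with a robust 95% CI. Do this for both HIV-1 RNA thresholds, and show the crude difference and its CI beside it.
2. **Section 5, covariates.** List them, restrict them to values on or before randomization, and give a simple rule for missing baseline HIV-1 RNA.
3. **Section 5, purpose.** Replace the check for a change in the association with precision for the same estimand. Report any further adjusted analyses as risk differences as well.
4. **Section 6.1.** Carry the same adjustment to Weeks 24, 36 and 48.
5. **Section 4.1.** Amend the sentence that excludes adjustment for the age stratum.
6. **Section 1.2.** Record when the change was made relative to review of outcome data. If analysis had already begun, label it post hoc, as Section 4.1 already requires for outcome measures.

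The cost is SAP wording and a few lines of code. No new data collection is needed. A working model is required, although the standardised difference remains valid in large samples under randomization if that model is wrong. There is a slight loss of precision if the covariates are not prognostic, and a late change of main estimator has to be explained.
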